11.1 Adverse Events

11.1.1 Reportable AEs

Subjects must be carefully monitored for adverse events. The ADVERSE EVENT-REPORTING PERIOD for this study begins upon signing the informed consent form and ends 30 days after the study period. All AEs that occur after the informed consent is signed and baseline assessments are completed (including run-in) must be recorded on the AE CRF (paper and/or electronic) whether or not related to study agent.

IN ADDITION, any known untoward serious event that occurs subsequent to the adverse event reporting period that the Investigator assesses as possibly related to the investigational medication/product should also be reported if the incident meets the definition of an adverse event.

11.1.2 AE Data Elements:

The following data elements are required for adverse event reporting.

- AE verbatim term
- System Organ Class (SOC)
- Common Terminology Criteria for Adverse Events v4.0 (CTCAE) AE term
- Event onset date and event ended date
- Severity grade
- Attribution to study agent (relatedness)
- Whether or not the event was reported as a serious adverse event (SAE)
- Whether or not the subject dropped due to the event
- Outcome of the event

11.1.3 Severity of AEs

11.1.3.1 Identify the AE using the NCI Common Terminology Criteria for Adverse Events (CTCAE) version 4.0. The CTCAE provides descriptive terminology and a grading scale for each adverse event listed.

A copy of the CTCAE can be found at

http://ctep.cancer.gov/protocolDevelopment/electronic_applications/ctc.htm

AEs will be assessed according to the CTCAE grade associated with the AE term. AEs that do not have a corresponding CTCAE term will be assessed according to the general guidelines for grading used in the CTCAE v4.0. as stated below.

CTCAE v4.0 general severity guidelines:

Grade	Severity	Description
1	Mild	Mild; asymptomatic or mild symptoms; clinical or diagnostic observations only; intervention not indicated.
2	Moderate	Moderate; minimal, local or noninvasive intervention indicated; limiting age-appropriate instrumental activities of daily living (ADL)*.
3	Severe	Severe or medically significant but not immediately life-threatening; hospitalization or prolongation of hospitalization indicated; disabling; limiting self-care ADL**.
4	Life-threatening	Life-threatening consequences; urgent intervention indicated.
5	Fatal	Death related to AE.

ADL

*Instrumental ADL refers to preparing meals, shopping for groceries or clothes, using the telephone, managing money, *etc.*

**Self-care ADL refers to bathing, dressing and undressing, feeding self, using the toilet, taking medications, and not bedridden.

11.1.4 Assessment of relationship of AE to treatment

The possibility that the adverse event is related to study agent will be classified as one of the following: not related, unlikely, possible, probable, definite.

11.1.5 Follow-up of AEs

All AEs, including lab abnormalities that in the opinion of the investigator are clinically significant, will be followed according to good medical practices and documented as such.

11.2 Serious Adverse Events

11.2.1 DEFINITION: Fed. Reg. 75, Sept. 29, 2010 defines SAEs as those events, occurring at any dose, which meet any of the following criteria:

- Results in death
- Is life threatening (*Note: the term life-threatening refers to an event in which the patient was at risk of death at the time of the event; it does not refer to an event which hypothetically might have caused death if it were more severe*).
- Requires inpatient hospitalization or prolongation of existing hospitalization
- Results in persistent or significant incapacity or substantial disruption of the ability to conduct normal life functions
- Is a congenital abnormality/birth defect
- Important medical events that may not result in death, be life-threatening or require hospitalization may be considered serious when, based upon appropriate medical judgment, they may jeopardize the patient or subject and may require medical or surgical intervention to prevent one of the outcomes listed.

11.2.2 Reporting SAEs

11.2.2.1 The Lead Organization and all Participating Organizations will report SAEs on the DCP SAE form found at http://prevention.cancer.gov/files/clinical-trials/SAE_form.doc.

11.2.2.2 Contact the DCP Medical Monitor by phone or email within 24 hours of knowledge of the event.

NCI/Division of Cancer Prevention
[name]
Lung & Upper Aerodigestive Cancer Research Group
Division of Cancer Prevention, NCI, NIH
[name]
[name]
[contact]
[contact]
email: [contact]

Include the following information when calling the Medical Monitor:

- Date and time of the SAE
- Date and time of the SAE report
- Name of reporter
- Call back phone number
- Affiliation/Institution conducting the study
- DCP protocol number
- Title of protocol
- Description of the SAE, including attribution to drug and expectedness

11.2.2.3 The Lead Organization and all Participating Organizations will FAX written SAE reports to the DCP Medical Monitor [contact]) within 48 hours of learning of the event using the paper SAE form. The written SAE reports will also be FAX'ed [contact]) or emailed ([contact]) to DCP's Regulatory Contractor, CCS Associates ([contact]).

11.2.2.4 The DCP Medical Monitor and regulatory staff will determine which SAEs require FDA submission.

11.2.2.5 The Lead Organization and all Participating Organizations will comply with applicable regulatory requirements related to reporting SAEs to the IRB/IEC.

11.2.3 Follow-up of SAE

Site staff should send follow-up reports as requested when additional information is available. Additional information should be entered on the DCP SAE form in the appropriate format. Follow-up information should be sent to DCP as soon as available. SAE will be followed until resolved, or deemed unlikely to further resolve by the Protocol Chair, or until the subject withdraws consent for further follow-up. SAE unrelated or unlikely to be related to study agent will be followed for at least 30 days after the last dose of study agent.

12. STUDY MONITORING

12.1 Data Management

This study will report clinical data using the OnCore application from Forte Research Systems, Inc., as stated in the Master Data Management Plan. All users of the database will have appropriate education, training and experience to perform assigned tasks. The data collection and management will be done according to the Consortia 2012 DMP.

12.2 Case Report Forms

Participant data will be collected using protocol-specific case report forms (CRF) developed from the standard set of DCP Chemoprevention CRF Templates and utilizing NCI-approved Common Data Elements (CDE). The approved CRFs will be used to create the electronic CRF (e-CRF) screens in the OnCore application. Site staff will enter data into the e-CRF for transmission to DCP according to pre-established DCP standards and procedures. Amended CRF will be submitted to the DCP Protocol Information Office for review and approval. Approved changes will be programmed into the OnCore database by the Consortium Data Management staff.

12.3 Source Documents

Source documentation for this trial will consist of protocol-specific source documents as well as clinical and research laboratory reports. In the event of a Serious Adverse Event, medical records related to the event will be sought for source documentation of the event and its treatment, if any.

12.4 Data and Safety Monitoring Plan

The University of Arizona Cancer Center (UACC) Data and Safety Monitoring Board (DSMB) will ensure subject safety by coordinating, monitoring, and providing oversight for study data and subject safety for all UA Consortium clinical trials consistent with the National Institutes of Health Policy for Data and Safety Monitoring dated June 10, 1998; further guidance statement issued by the NIH on June 5, 2000, and the policy for Data and Safety Monitoring by Data and Safety Monitoring Boards. Data from this study will be

monitored by the UACC DSMB every six months.

Regular monthly meetings of the UA Consortium, are used as a forum to review accrual rates, problematic issues relating to accrual and protocol implementation, adverse events occurrence, follow-up, and reporting; submission of all required study reports; and progress and outcomes of laboratory analyses.

12.5 Sponsor or FDA Monitoring

The NCI, DCP (or their designee), pharmaceutical collaborator (or their designee), or FDA may monitor/audit various aspects of the study. These monitors will be given access to facilities, databases, supplies and records to review and verify data pertinent to the study.

12.6 Record Retention

Clinical records for all participants, including CRFs, all source documentation (containing evidence to study eligibility, history and physical findings, laboratory data, results of consultations, *etc.*), as well as IRB records and other regulatory documentation will be retained by the Investigator in a secure storage facility in compliance with Health Insurance Portability and Accountability Act (HIPAA), Office of Human Research Protections (OHRP), Food and Drug Administration (FDA) regulations and guidances, and NCI/DCP requirements, unless the standard at the site is more stringent. The records for all studies performed under an IND will be maintained, at a minimum, for two years after the approval of a New Drug Application (NDA). For NCI/DCP, records will be retained for at least three years after the completion of the research. NCI will be notified prior to the planned destruction of any materials. The records should be accessible for inspection and copying by authorized persons of the Food and Drug Administration. If the study is done outside of the United States, applicable regulatory requirements for the specific country participating in the study also apply.

12.7 Cooperative Research and Development Agreement (CRADA)/Clinical Trials Agreement (CTA)

Not applicable.

13. STATISTICAL CONSIDERATIONS

13.1 Study Design/Description

This study utilizes a Phase II, randomized, placebo-controlled design in order to assess the effect of the combination of ASA and zileuton to decrease biases (participant and investigator-derived) that would potentially influence the reporting and interpretation of the data. Each eligible participant will be randomly assigned to receive either ASA and zileuton or placebo.

The primary endpoint analysis will use a previously developed nasal gene expression signature for tobacco smoke exposure as reported by Zhang et al.³⁴ The signature is composed of 119 genes whose expression is altered in both the bronchial and nasal epithelium of current versus never smokers. The first principal component from a principal component analysis across the 119 genes and nasal data from Zhang et al. was used to compute a smoking signature score for each of the samples in Zhang et al. and in an independent cohort of 130 nasal samples from current and former smokers. The nasal smoking signature was able to significantly separate never or former smokers from current smoker ($p < 0.01$, see Figure 1).

[figure not shown]

Figure 1. The smoking gene signature score separates never or former smokers from current smokers. The score is significantly different between the two groups in all three analyses by the Wilcoxon rank sum test ($p < 0.01$).

13.2 Randomization/Stratification

Each eligible participant will be randomly assigned to receive ASA + zileuton or placebo based on a random allocation rule. In addition, the randomization will be stratified on gender to assure that equal number of males and females assigned to receive either ASA + zileuton or placebo. No blocking technique will be used.

13.3 Accrual and Feasibility

We plan to randomize 66 eligible participants to receive either ASA + zileuton or placebo (33 per group). With an estimated attrition rate of 38.5% for men and 26.7% for women (with respect to endpoint data), we expect to have at least 20 participants (10 males and 10 females) per group with evaluable endpoint data. We anticipate to enroll 3-4 participants/per month and estimate it will take approximately 18 months to complete accrual.

13.4 Primary Objective, Endpoint(s), Analysis Plan

The primary endpoint of this study is to compare changes in a smoking-related gene expression signature score in the nasal epithelium of current smokers after ASA and zileuton intervention. We propose to use the smoking gene signature score to assess the impact of ASA and zileuton on smoking-related nasal gene expression. A two-sided two-sample t test will be used to test whether or not there are significant differences in changes in smoking gene signature score (changes from baseline) between the treatment and placebo groups. Based on a sample size of 20 per group, the power will be at least 85% to detect an effect size of ≥ 1 (i.e. \geq one standard deviation difference in the mean changes between the two groups) at a significance level of 5%. Exploratory analyses will be performed to evaluate whether the effect of ASA and zileuton on smoking-related gene expression signature is modulated by gender and whether gene expression changes are associated with ASA and zileuton exposure and changes in PGE-M and LTE(4) levels.

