7.3 Evaluation During Study Intervention

Study participants will return to the clinic for baseline specimen collection (Visit 2). During the visit, weight, blood pressure, pulse, temperature will be measured. A blood sample will be collected for plasma salicylate, ASA, zileuton levels and AA oxylipin analysis. Urine will be collected for PGE-M, LTE(4), and cotinine levels. If urine cotinine level was collected at the screening visit, it will serve as the baseline and will not be repeated at baseline visit. Participants will undergo a baseline nasal epithelium collection via cytology brushing of the nasal turbinate (see Section 7.6) for gene expression analysis. Buccal cells will also be collected (see Section 7.6) and archived as a reserved specimen for gene expression analysis and karyometric analysis. Women of childbearing potential will have urine pregnancy tests prior to receiving study agent at Visits 1 and 2 and also at Visits 3, 4, and 5.

Post baseline specimen collection, participants will be randomized to receive ASA 81 mg daily + Zileuton (Zyflo) 2 x 600 mg BID or placebos for 3 months. Participants will be supplied with a 6-week supply of study agents (to ensure sufficient agent supply until the interim visit), a study agents intake diary and AE diary.

Participants will return for two interim study visits (Visit 3, after 4±1 weeks of agent intervention and Visit 4, after 8±1 weeks of agent intervention). These visits will include vital signs, blood for hepatic panel, check of study agent intake, and a current tobacco use assessment. Concomitant medications and AEs will be

reviewed. Participants will return any unused study agents and receive the next 6-week supply of study agents.

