13.5 Secondary Objectives, Endpoints, Analysis Plans

The secondary endpoints are 1) To assess the impact of ASA and zileuton on three lung cancer gene signatures (an 80-gene bronchial signature, a PI3K pathway gene signature and a nasal diagnostic gene signature) and to compare this to placebo control; (2) To measure urinary PGE-M and LTE(4) levels in current smokers after ASA and zileuton; (3) To assess the safety in current smokers of 12 week exposure to ASA and zileuton; (4) To evaluate a gender effect in the modulatory effects of ASA and zileuton on smoking-related gene expression signature; (5) To explore the effect of ASA and zileuton on the metabolomics profile of the arachidonic acid pathway; and (6) To explore, in a discovery-driven fashion, the effect of ASA and

zileuton on whole-genome gene expression.

For the secondary endpoints, ANOVA will be performed to evaluate whether ASA and zileuton has significantly different impact on changes in the three lung cancer gene signatures and the changes are significantly different from the placebo group. Two sample t tests will be performed to evaluate whether or not there are significant differences in changes in PGE-M, LTE(4) and oxylipin metabolome, respectively, between the treatment and placebo groups. In addition, system biology methods will also be used to analyze the oxylipin metabolome data. Pair-wise comparisons based on two-sample t tests will be performed to whole-genome gene expression data to identify the genes for which ASA and zileuton has a significantly different expression level from the placebo group. Multivariate statistical techniques such as principle component analysis (PCA) will be used to reduce complexity of the whole-genome expression data. PCA analysis will help to identify the major analytes driving a process. For all of the secondary and exploratory analyses, adjustment for multiple comparisons will not be performed. However, the number of comparisons will be reported and we will also cautiously interpret the findings. For both primary and secondary endpoints, if the normality assumption is violated, potential transformation will be sought or nonparametric methods such as Wilcoxon rank sum and Kruskal Wallis tests will be performed.

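### The primary t test on change uses baseline only by subtraction and omits the stratification factor; ANCOVA would usually be more precise and costs about 1 point of power at worst

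*Combined protocol and SAP*

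**What the plan says.** Section 13.4 gives the primary analysis: "A two-sided two-sample t test will be used to test whether or not there are significant differences in changes in smoking gene signature score". The score is analysed as change from baseline, the comparison is between the two arms, and no covariate is named. The sample size statement takes 20 per group, a difference of one standard deviation (SD) of the change score and a two-sided 5% level, and claims power of at least 85%.

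Section 13.2 states that "the randomization will be stratified on gender". Section 13.3 adds: "we expect to have at least 20 participants (10 males and 10 females) per group with evaluable endpoint data". A baseline measurement is built into the schedule; Section 7.3 says: "Participants will undergo a baseline nasal epithelium collection via cytology brushing of the nasal turbinate".

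Nothing else adjusts the primary comparison. The gender analysis in 13.4 is exploratory and asks whether gender modifies the effect; 13.5 lists the same question as a secondary endpoint. The fallback in 13.5, which covers primary and secondary endpoints, reads: "if the normality assumption is violated, potential transformation will be sought or nonparametric methods such as Wilcoxon rank sum". It names no covariates either.

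**The concern.** Subtracting the baseline amounts to a regression on baseline with the slope set to 1. When the true slope is not 1, this leaves avoidable noise in the comparison and does not fully correct a chance baseline imbalance between arms. ANCOVA estimates the slope from the data. In large samples its variance is never above that of the change-score comparison.

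Gender is a separate matter. Stratifying balances it between the arms, but if gender affects change, an analysis that ignores it leaves that variation in the error term and the test becomes conservative.

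The trial is small and expects to lose endpoint data on 38.5% of men and 26.7% of women (13.3). Precision that is available at almost no cost is therefore worth having.

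**Working it through.** **Inputs from the documents.** 20 evaluable per arm, 10 men and 10 women (13.3); difference of 1 SD of change, two-sided 5% (13.4); 18 men and 15 women randomised per arm (Section 3).

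**Inputs assumed, because the documents do not give them.** The baseline to week-12 correlation r, and k, the ratio of the week-12 SD to the baseline SD.

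**Step 1: the plan's own figure.** Noncentral t, 38 degrees of freedom, noncentrality 1/√(2/20) = 3.16: power 86.9%. The claim of at least 85% is right.

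**Step 2: variance of ANCOVA relative to the change score.**

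V = (1 − r²)k² / (1 + k² − 2rk)

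V is at most 1, and equals 1 when r × k = 1. With k = 1 it reduces to (1 + r)/2.

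**Step 3: power of ANCOVA with baseline and gender.** There are 40 − 4 = 36 degrees of freedom. Estimating the baseline slope inflates the variance by about 1 + 1/35. The noncentrality is 1/√(V × (2/20) × (1 + 1/35)). At r = 0.5 and k = 1, V = 0.75 and the noncentrality is 1/√(0.75 × 0.1 × 1.0286) = 3.60, giving 93.9%. The t test has 86.9% in every row below.

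| Case | V | ANCOVA power | CI width, ANCOVA / t test |
|---|---|---|---|
| r = 0.3, k = 1 | 0.65 | 96.4% | 0.82 |
| r = 0.5, k = 1 | 0.75 | 93.9% | 0.88 |
| r = 0.7, k = 1 | 0.85 | 90.8% | 0.94 |
| r = 0.9, k = 1 | 0.95 | 87.5% | 0.99 |
| Worst case, r × k = 1 | 1.00 | 85.9% | about 1.016 |

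The width ratios come from simulating the full model (10 men and 10 women per arm, no gender effect on change). Simulated power agreed with the formula: 96.5%, 93.8%, 91.0% and 87.7% in the first four rows, and 85.8% at r = 0.8, k = 1.25. Rejection under the null was 4.9% to 5.3% across all settings.

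**Step 4: unequal SDs.** At k = 0.8, r = 0.5: V = 0.75 × 0.64 / (1 + 0.64 − 0.80) = 0.57, with simulated power 97.9%. At k = 1.25, r = 0.8: V = 0.36 × 1.5625 / (1 + 1.5625 − 2) = 1.00, so the gain vanishes.

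**Step 5: the sample size implied by the plan's attrition.** 18 × 0.615 + 15 × 0.733 = 11.07 + 11.00 = 22.1 per arm. At 22, the t test has 90.0%. ANCOVA, after the slope cost, has 97.7%, 95.8%, 93.4% and 90.6% at r = 0.3, 0.5, 0.7 and 0.9 (k = 1), and 89.2% in the worst case.

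**Step 6: what gender could add.** Suppose baseline adds nothing, gender shifts the change by 0.5 or 1 within-gender SD, and the treatment effect is 1 within-gender SD. The unadjusted t test then has 85.4% or 81.1% power; the adjusted model has about 86% in both cases. The documents give no gender difference in change, so these cases only illustrate the point.

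**The case against.** The strongest reply is that nothing in the plan is wrong. The endpoint is defined as a change, the test compares changes, the power statement uses the SD of change, and the plan meets its own target. That stands: this is an efficiency point, not an error.

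The size of the gain rests on r and k, which the documents do not supply. Within the assumed range at k = 1 it runs from 9.5 points of power (r = 0.3) to 0.6 (r = 0.9), and it becomes a 1-point loss when r × k = 1. That also stands, and is why a range is shown. It does not defeat the point, because the downside is bounded. At a 1-SD effect the loss is at most 1.0 point; over effects from 0.3 to 1.55 SD it is at most 1.3 points, at 0.8 SD.

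The benefit of including gender is not established. Subtraction already removes a stable gender difference in level, so only a gender difference in change would matter. The case for including it is that the analysis should follow the randomisation, at a cost of one degree of freedom.

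Finally, a model on ranks gives a test but no difference in score units, and the fallback in 13.5 already lists transformation and does not limit the plan to the Wilcoxon test. Both are fair limits on the fallback. The main change does not depend on it.

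**Conclusion.** The concern holds as a nearly free improvement to a valid analysis; the change should be made, but the plan is not unsound without it. With 20 per arm, a 1-SD effect and equal SDs, ANCOVA raises power from 86.9% to between 87.5% and 96.4% for r from 0.9 down to 0.3. If the covariates explain nothing, power is 85.9%, so the plan's claim of at least 85% survives the change even then. The algebra and the bound on the loss are firm. The actual gain in this trial depends on r, k and the gender effect on change, none of which the documents give.

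**What to change.** In 13.4, prespecify as primary an ANCOVA of the week-12 signature score on arm, baseline score and gender. Using change as the outcome gives the same arm difference. Report the adjusted difference with a 95% confidence interval and a two-sided test at 5%. Keep the unadjusted t test on change as a sensitivity analysis.

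In 13.5, use the same model for each of the three lung cancer signature scores. If normality fails, fit it to transformed scores, or to ranked scores for the test alone, in place of an unadjusted Wilcoxon test.

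Settle this before unblinding, so that the choice of covariates cannot appear driven by the results. The cost is a few sentences in 13.4 and 13.5 and two degrees of freedom. No new data or participants are needed.
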